### Concealment of allocation

The participants will not be aware of intervention allocation before and during the trial as they will be invited to participate in research about the readability of new Cochrane formats.

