### Objectives

The objective of our study is to evaluate the efficacy of infographics in presenting information, in terms of understanding and remembering research results, compared to standard PLS formats and scientific summary format.

The null hypothesis is that the proportion of the correct answers in all three groups is not going to differ significantly. The equation for that hypothesis is:

$$H_0: \text{Infographic} = \text{PLS} = \text{SciSumm}$$

The alternative hypothesis is that participants in the infographic group (Infographics) will have significantly more correctly answered questions about the topic than those in PLS group (PLS), meaning that infographics enables a better understanding of scientific findings than PLS. Also, the scientific summary group will have the lowest knowledge score of the three groups, meaning that scientific summary is not the suitable way of data presentation about a Cochrane review for lay population. The equation for that hypothesis is:

$$H_a: \text{Infographic} > \text{PLS} > \text{SciSumm}$$

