### Interventions

Infographics format of a Cochrane systematic review summary represents the experimental intervention in the trial. The control groups will receive either PLS (which represent text format with simple explanation of the survey topic main findings and is intended for lay audience) or the scientific summary (the text written for the academic population and practitioners) groups. We will use formats already available for the systematic review on external cephalic version for breech presentation before term (Hutton et al, 2015.).

All three types of Cochrane summaries will be translated into Croatian by the trial organizers, and back translated to English by an independent language expert to ensure the quality of the Croatian translation. The survey instrument will be in Croatian.

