### Blinding

Participants will not be blinded to type of format, but the authors who analyse the answers will be blinded to the type of formats.

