#### Claiming of the non-inferiority

For the primary outcome, non-inferiority of the experiment format to the control formats will be claimed if the lower limit of the CI (for the difference in average results between intervention group and control groups) is higher than the non-inferiority margin of 20%. The tests of superiority will be applied to the secondary outcomes. We want to perform the non-inferiority testing in order to prove that infographic is no worse than PLS and scientific summaries for information translation in terms of understanding of information. Also, the superiority tests will show that the infographic is better in terms of user satisfaction and accessibility of information compared to standard PLS and scientific summaries.

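### The invitation to research on new formats may give unblinded doctors different expectations by arm and so affect the self-rated superiority outcomes; neutral wording would avoid this

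*Combined protocol and SAP*

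**What the plan says.** Concealment of allocation makes one claim, "The participants will not be aware of intervention allocation before and during the trial", and supports it with one measure: "they will be invited to participate in research about the readability of new Cochrane formats". The next section, Blinding, states "Participants will not be blinded to type of format" and adds that "the authors who analyse the answers will be blinded to the type of formats".

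Interventions names the experimental arm: "Infographics format of a Cochrane systematic review summary represents the experimental intervention in the trial". It also says of all three summaries that "We will use formats already available for the systematic review". The Objectives set the infographic against its comparators in the words "compared to standard PLS formats and scientific summary format".

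The outcomes at issue are reading experience (Survey C1) and accessibility of information (Survey C2). Each is the sum of five self-rated items scored 1 to 10. Under Claiming of the non-inferiority, secondary outcomes are to be tested for superiority, and the plan expects that "the superiority tests will show that the infographic is better in terms of user satisfaction and accessibility of information".

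**The concern.** There are two linked problems.

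First, the reason given for unawareness does not support the claim. An invitation can keep people from knowing beforehand what they will receive. It cannot keep someone who is reading an infographic from knowing that it is one, and the Blinding section accepts this.

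Second, the invitation is the only measure described for managing participants' expectations, and it carries the word *new*. If that word suits one arm better than the others in readers' eyes, it can shift ratings for reasons unrelated to how well the format works. C1 and C2 are exposed because the participant is the assessor, so blinding the authors who analyse the answers gives no protection. At stake is whether a difference on these scales can be read as an effect of the format.

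**Working it through.** The plan gives no figure on this point, so the main check is to read the sections together.

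1. **What participants know.** Concealment of allocation claims unawareness before and during the trial. Blinding says format is not masked. Both can hold only if *allocation* means which format is experimental, or which formats are being compared. The plan does not say so.
2. **Who the participants are.** Eligibility criteria recruits doctors from a list of clinical researchers at a medical school and a university hospital. Interventions describes the scientific summary as written for academics and practitioners, which is this group. Outcomes records prior experience with Cochrane reviews and the Cochrane Library, so some familiarity is foreseen.
3. **How the cue could differ by arm.** Each participant sees one format (Trial design), so no comparison is possible within the survey. Familiarity comes from outside it. A doctor told to expect something new who opens a conventional summary may recognise it as established. One who opens an infographic has less reason to. The same invitation can then set different expectations in different arms.
4. **What it could reach.** C1 and C2 totals run from 5 × 1 = 5 to 5 × 10 = 50. They are compared between groups by ANOVA or Kruskal-Wallis (Inferential statistics). An expectation shift and a format effect both appear as a between-group difference, so neither test can separate them.

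**Illustration only, with assumed shifts.** The check simulated 20,000 trials per setting: three equal groups, normal ratings with SD 1, no true format effect, and the infographic mean moved by *b* SD. It used a one-way ANOVA and a two-sided t-test of the infographic against one control, both at 0.05. Fifteen per group is the Sample size figure, taken as stated; 30 is an assumed larger size.

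| *b* (SD) | ANOVA significant, 15/group | t-test favours infographic, 15/group | ANOVA significant, 30/group |
|---|---|---|---|
| 0 | 5.0% | 2.5% | 4.9% |
| 0.2 | 8.0% | 7.7% | 10.8% |
| 0.3 | 11.5% | 12.0% | 19.8% |
| 0.5 | 26.1% | 26.2% | 48.5% |
| 0.8 | 58.4% | 56.6% | 89.8% |

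By symmetry, a negative *b* gives the same ANOVA rates against the infographic. The table shows that a shift, if there is one, is not averaged away by a larger sample. It is not evidence that a shift exists.

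**The case against.** The strongest objection is that the labels *standard* and *experimental* are in the protocol, and nothing shows that participants see either. The invitation as described uses a plural, does not name the infographic and is the same in every arm. All three formats already exist. A reader of the PLS or the scientific summary could equally take theirs to be the new one, and the cue would then be similar across arms. The full invitation text is not in the documents, so one clause of description stands in for it.

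Most of this stands. A reader might infer that the wording marks the infographic as the product under test and biases the ratings in its favour. The documents do not support that. The direction is open too: a promise of novelty could raise expectations and lower infographic ratings, or make control readers generous. A reader might also infer an effect on effort in the knowledge test, and nothing in the documents bears that out. What survives is narrower. In a sample of doctors, some of whom know Cochrane material, equal effects across arms cannot be assumed.

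It is also fair to say that the two sections can be read together as meaning that participants see their format but do not know which one is experimental. That reading is sensible, but the plan should state it.

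Finally, neutral wording blinds nobody, and other features may matter more. C1 item 3, reverse scored, asks whether the reader wanted more pictures or graphs. It can contribute up to 9 of the 45 points of C1's range whatever the invitation says. That is a separate point and does not remove this one.

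**Conclusion.** The concern holds as a cheap, avoidable risk to two secondary outcomes. It is not a demonstrated bias. Two things are firm: the invitation does not justify the claim of unawareness during the trial, and C1 and C2 are rated by unblinded participants who have been told to expect something new. That expectations differ by arm is plausible but inferred. Its size and direction cannot be derived from the documents, and zero is among the possibilities.

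The inference assumes that the description of the invitation is close to its actual wording. It also assumes that the participants are doctors, as Trial design and Eligibility criteria say. Participant timeline, Sequence generation and Data Management still describe students, among whom familiarity with existing formats might be lower. The point does not extend to the knowledge score or the numeracy test.

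**What to change.** - **Invitation.** Use wording that fits all three arms and omits *new*, for example: *research on how summaries of Cochrane reviews are understood*.
- **Concealment of allocation and Blinding.** Reconcile the two by replacing the claim of unawareness during the trial with a statement such as: *participants see their assigned format but are not told which formats are compared or which is experimental*.
- **Debrief.** Disclose the full comparison in a short text at the end of the survey.
- **Limitation.** State that participants remain unblinded, so any novelty effect of the infographic itself cannot be separated from its effect on C1 and C2.

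The cost is one sentence in the invitation, one or two in the protocol, and the debrief text. Sample size, outcomes and analysis are unchanged. The downside is that participants learn of the comparison only afterwards, so the ethics committee should see the revised invitation and the debrief.

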### Blinding

Participants will not be blinded to type of format, but the authors who analyse the answers will be blinded to the type of formats.

### **Methods: Data collection, management, and analysis**

Data will be collected electronically, using the SurveyMonkey platform. The data will be fully anonymous and will be kept on a secure server of the School of Medicine.

#### Descriptive statistics

Descriptive statistics will include participants' baseline characteristics and outcomes, means and standard deviations for continuous variables and proportions for dichotomous variables.

#### Claiming of the non-inferiority

For the primary outcome, non-inferiority of the experiment format to the control formats will be claimed if the lower limit of the CI (for the difference in average results between intervention group and control groups) is higher than the non-inferiority margin of 20%. The tests of superiority will be applied to the secondary outcomes. We want to perform the non-inferiority testing in order to prove that infographic is no worse than PLS and scientific summaries for information translation in terms of understanding of information. Also, the superiority tests will show that the infographic is better in terms of user satisfaction and accessibility of information compared to standard PLS and scientific summaries.

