### Sample size

The sample size was calculated using the Sample Size Calculator (Medcalc, Ostend, Belgium).

We calculated the sample size based on the main outcome of the study: score on the knowledge/understanding test. We used the alpha of 0.05 and 80% power to detect the difference of average result in groups of people who correctly answered the questions. We used the data from the studies by Santesso et al. (2015) and Schwartz et al.(2009) to estimate that the difference of 40% in the knowledge score would be the size of effect relevant for our study. In those studies, 80% of the participants who received a summary of information in a table with event rates answered questions correctly compared with 20-40% of those who did not receive this information. We thus estimated that, at a minimum, 15 people in each group need to complete the survey so it can be compared between with the other group.

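### The plan sets incompatible success criteria for the knowledge score: ordered superiority in the objectives and sample size, non-inferiority in the claim rule, and an omnibus test in Table 1

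*Combined protocol and SAP*

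**What the plan says.** All of the following concern the primary outcome, the 0 to 10 knowledge score.

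- **Objectives.** Under the null, "the proportion of the correct answers in all three groups is not going to differ significantly". Under the alternative, the infographic group "will have significantly more correctly answered questions about the topic than those in PLS group (PLS", and "the scientific summary group will have the lowest knowledge score of the three groups". The displayed alternative is Infographic > PLS > SciSumm.
- **Sample size.** Alpha is 0.05, with "80% power to detect the difference of average result in groups". It adds that "the difference of 40% in the knowledge score would be the size of effect relevant for our study". The result is at least 15 per group. No margin enters the calculation.
- **Claiming of the non-inferiority.** The rule begins: "For the primary outcome, non-inferiority of the experiment format to the control formats will be claimed if the lower limit of the CI". That limit belongs to intervention minus control, and the claim is made when it "is higher than the non-inferiority margin of 20" per cent. The section goes on: "The tests of superiority will be applied to the secondary outcomes". The stated purpose is to show that the infographic does not do worse than either control.
- **Inferential statistics, Table 1.** Kruskal-Wallis/ANOVA is the only method listed to compare formats on understanding. The text above the table plans that choice only for reading experience and accessibility. Logistic regression on demographics and the Spearman correlation with numeracy do not compare formats.

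**The concern.** Three different questions are put to one primary outcome. Is the infographic better than PLS, and PLS better than the scientific summary? Is the infographic not worse than either? Do the three formats differ at all? Each can have a different answer in the same data, and the plan does not say which one decides the trial.

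Non-inferiority followed by superiority is a legitimate design, but no such sequence is stated. The only sentence that allocates superiority tests gives them to the secondary outcomes. No directional test is planned for Infographic > PLS or PLS > SciSumm on understanding.

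At stake is the freedom to choose the success criterion after the results are known.

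**Working it through.** **1. The plan's own figure.** The usual two-sided formula for two proportions (alpha 0.05, 80% power) is n = [1.96·√(2p̄(1−p̄)) + 0.842·√(p1(1−p1)+p2(1−p2))]² / (p1−p2)².

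- 80% vs 40% (the stated 40-point difference): [1.96·√0.48 + 0.842·√0.40]² / 0.16 = 22.3, so 23 per group. The stated 15 is not reproduced.
- 80% vs 30% (the middle of the quoted 20-40%): [1.96·√0.495 + 0.842·√0.37]² / 0.25 = 14.3, so 15 per group.
- Read as 4 of 10 points, 15 per group at 80% power implies SD = 4 / [(1.96+0.842)·√(2/15)] = 3.9, or about 3.8 with the t distribution.

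Every route found to about 15 is a two-group superiority calculation. None uses the 20% margin.

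**2. One data set under each rule.** Assume SD 2 in each arm, 15 per arm, 95% t intervals (28 df, t = 2.048) and a margin of 2 of 10 points. The half-width is 2.048 × 2 × √(2/15) = 1.50 points. If the three observed means are equal, every pairwise interval is (−1.50, +1.50).

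| Rule | Requirement | Met? |
|---|---|---|
| Non-inferiority, margin as intended | lower limit > −2 | yes |
| Non-inferiority, margin as printed | lower limit > +2 | no |
| Ordered superiority (Objectives) | lower limits > 0, in order | no |
| Omnibus test (Table 1) | significant | no (F = 0) |

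The observed difference needed in a single comparison is −2 + 1.50 = −0.50 for the intended margin, +1.50 for superiority and 2 + 1.50 = +3.50 for the printed margin. In the other direction, an omnibus test can be significant because the infographic scored lowest. The null is then rejected, yet neither claim is supported.

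**3. How often.** Normal scores, 15 per arm, 95% intervals, margin −2, 200,000 simulated trials per row. The superiority column uses the noncentral t. Every SD is an assumption.

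| SD | Non-inferior to both, true equality | One superiority comparison, true difference 4 points |
|---|---|---|
| 1.5 | 90% | >99.9% |
| 2 | 62% | >99.9% |
| 2.5 | 40% | 98.8% |
| 3 | 26% | 94% |
| 3.8 | 14-15% | 79% |

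The last row is roughly the SD implied in step 1. At true equality, non-inferiority to both is met together with a non-significant omnibus test in about 60% of trials at SD 2 and 38% at SD 2.5. With true means 8/6/4, the full order is shown in about 53% (SD 2) and 25% (SD 2.5).

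**The case against.** The strongest reply is that the parts can be read together. The Objectives, the sample size and Table 1 all point to a difference, so the non-inferiority section is the outlier and could simply be dropped. That section also describes an interval for a difference, so pairwise intervals do exist in the plan. An omnibus test in a summary table does not rule out pairwise follow-up. No informed reader would apply a +20% limit under a heading about non-inferiority. The unstated CI level and margin unit are gaps in detail, not errors.

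Much of this stands. Nothing ranks the non-inferiority section above the Objectives, so the remedy must leave superiority open as the primary aim. The sign is a notation error that is easily corrected. The CI level and unit are supporting detail only. What does not fall away is that the only written claim rule is for non-inferiority, that superiority is expressly assigned elsewhere, and that no text connects the two.

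A reader might also infer that 15 per group is too few for non-inferiority. The documents do not support that as a finding. It depends on an SD that they do not give: by the normal approximation, one comparison has 80% power at 15 per group if the SD is at most about 1.96 points (one-sided 0.025). Nor is 3.8 an estimate of the SD. It follows only if the 40% means 4 points, whereas the rates quoted as its source are proportions of participants.

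**Conclusion.** The concern holds, and it must be fixed because it affects the success criterion of the primary outcome. The objectives, sample-size basis, claim rule and listed test do not describe the same question, and opposite primary conclusions can each be defended from the text. In addition, the margin as printed requires superiority by more than 20%, against the section's own purpose.

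The contradiction rests on the text alone. The percentages rest on assumed SDs, normal scores, a 95% interval and a reading of 20% as 2 of 10 points. They show that the stated 80% power does not describe the non-inferiority claim. They do not show what its power actually is.

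**What to change.** Before any data are seen, the sponsor should choose one primary rule and align the Objectives, Sample size, Claiming of the non-inferiority and Table 1 with it.

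- **Option A, superiority primary** (closest to the Objectives, Sample size and Table 1). Test Infographic minus PLS, then PLS minus SciSumm, in fixed sequence. Each step needs the lower limit of the two-sided 95% CI above 0. Claim the order only if both succeed. Drop the non-inferiority rule for the primary outcome or make it secondary.
- **Option B, non-inferiority primary.** Claim it only if the lower 95% limits of both Infographic minus PLS and Infographic minus SciSumm exceed −20 percentage points of the maximum score (−2 of 10 points; the sponsor to confirm the unit). Then either reword the alternative in the Objectives, or test the order in the same fixed sequence only after non-inferiority is met.

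Neither option needs an alpha adjustment: both non-inferiority comparisons must pass, and the later steps follow a fixed order. The omnibus test may stay but must not by itself support the claim. Sample size should say that its 80% power refers to detecting a 40% difference and not to non-inferiority. Under Option B it should also give the power at 15 per arm under a stated SD.

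**Cost.** Wording only, with no new data items and no added enrolment if the less favourable power is accepted. If 80% power for non-inferiority to both controls is wanted at true equality, about 21 per arm (SD 2) or 32 per arm (SD 2.5) would be needed. The full ordered claim is also weakly powered at 15 per arm, as the 8/6/4 case shows.

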#### Inferential statistics

The primary outcome of the trial understands of research results presented in various summary formats by lay persons. Each question has a single possible answer and the participant's result is the sum of the correct answers. Also, it is possible to determine how each one of the demographic characteristics predicts correct answer on the knowledge test using logistic regression.

For overall reading experience and accessibility of information between group testing we plan to test the distributions of the variables, and then to choose the non-parametric test (Kruskall-Wallis test) if the distribution of results is not normal or to choose the parametric test (ANOVA) if the distribution of results is normal.

Table 1 Overview of the outcome measures

Outcome	Scale	Measure	Methods of analysis
Understanding	Dichotomous	Sum of correct answers	Kruskall-Wallis/ANOVA
Accessibility of information	Continuous	Likert-type scale from 1 to 10	Kruskall-Wallis/ANOVA
Reading experience	Continuous	Likert-type scale from 1 to 10	Kruskall-Wallis/ANOVA
Health numeracy	Dichotomous	Sum of correct answers	Kruskall-Wallis/ANOVA; Spearman correlation coefficient with understanding outcome

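### The non-inferiority rule for the primary outcome lacks a minus sign, so as printed it contradicts its own aim; it also conflicts with the superiority hypothesis stated for the same outcome

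*Combined protocol and SAP*

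**What the plan says.** All references are to the combined protocol and SAP.

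- *Claiming of the non-inferiority*: for the primary outcome, the claim is made if the lower limit of the interval for the difference in average results "is higher than the non-inferiority margin of 20" per cent. The purpose is to "prove that infographic is no worse than PLS and scientific summaries for information translation in terms of understanding of information". The section reserves superiority tests for the secondary outcomes. It gives no sign for the margin, no explicit order of subtraction (though it names the intervention group first), no confidence level, and no indication whether 20% is absolute or relative.
- *Outcomes*: the primary outcome is a ten-question knowledge test with one point per correct answer, so higher is better.
- *Objectives*: the null hypothesis is that "the proportion of the correct answers in all three groups is not going to differ significantly". The alternative is that "participants in the infographic group (Infographics) will have significantly more correctly answered questions about the topic than those in PLS group (PLS"), with the scientific summary lowest.
- *Sample size*: alpha 0.05 (sidedness not given) and 80% power, on the basis that "the difference of 40% in the knowledge score would be the size of effect relevant for our study". The result is that "at a minimum, 15 people in each group need to complete the survey".
- *Inferential statistics*, "Table 1 Overview of the outcome measures": Understanding is assigned Kruskal-Wallis or ANOVA and nothing else.

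**The concern.** A non-inferiority claim on a score where higher is better needs the lower limit of (new minus control) to lie above a negative number. The printed threshold is positive. Taken at face value, this turns a claim of being no worse into a claim of being better by a margin, and it would refuse the claim to an infographic that performs exactly as well as the comparators. This is the only decision rule the plan gives for its primary claim.

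A second difficulty sits beside it. *Claiming of the non-inferiority* treats the primary outcome as a non-inferiority question. *Objectives* and *Sample size* treat it as a superiority question, and Table 1 offers only tests of equality across three groups, which do not compare anything with a margin. A reader cannot tell which analysis delivers the primary conclusion, or whether superiority on the primary outcome is to be tested formally at all.

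**Working it through.** **1. Direction (needs no assumption).** Let D = mean(infographic) − mean(control), and let L be the lower limit.

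- L(D) > +20%: the infographic is better by more than 20%. This is superiority by a margin.
- Reverse subtraction, L(−D) > +20%: the control is better by more than 20%. This does not fit the aim either.
- L(D) > −20%: the infographic is worse by less than 20%. This is the stated aim.

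**2. The plan's own figure of 15 per group.** The pooled two-proportion formula, two-sided alpha 0.05 and 80% power, is

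n = [1.96·√(2p̄(1−p̄)) + 0.842·√(p₁(1−p₁) + p₂(1−p₂))]² / (p₁−p₂)²

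- 80% v 40%: (1.358 + 0.532)²/0.16 = 22.3, so 23.
- 80% v 30%: (1.379 + 0.512)²/0.25 = 14.3, so 15.
- 80% v 20%: 10.

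So 15 is not recovered for the stated 40-point difference. It appears at 30%, the midpoint of the cited range ("answered questions correctly compared with 20-40% of those who did not receive this information"), which is a 50-point difference. That is a separate matter on which this point does not depend. What matters here is that the 20% margin is not an input to the sample size.

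**3. Size of the effect.** Assumptions not in the document: two-sided 95% interval, score as a percentage of maximum, SD 15, 20 or 25 points, margin in percentage points. From the document: at least 15 per group, a planned difference of 40, a margin of 20.

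SE = SD·√(2/n). With n = 15, df = 28 and t = 2.048, the half-width is t·SE. The probability that L exceeds a threshold θ at true difference δ is the upper tail of a noncentral t beyond t, with noncentrality (δ − θ)/SE.

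| | SD 15 | SD 20 | SD 25 |
|---|---|---|---|
| SE | 5.48 | 7.30 | 9.13 |
| Half-width | 11.2 | 15.0 | 18.7 |
| Observed D needed, θ = +20 | +31.2 | +35.0 | +38.7 |
| Observed D needed, θ = −20 | −8.8 | −5.0 | −1.3 |
| P(claim), θ = +20, δ = 0 | 2×10⁻⁸ | 2×10⁻⁶ | 2×10⁻⁵ |
| P(claim), θ = +20, δ = +20 | 2.5% | 2.5% | 2.5% |
| P(claim), θ = +20, δ = +40 | 94% | 75% | 56% |
| P(claim), θ = −20, δ = 0 | 94% | 75% | 56% |

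The last two rows agree because δ − θ = 20 in both: 40 − 20 = 0 − (−20). All figures are per comparison.

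**4. Sensitivity.** Fifteen is a minimum. At 30 per group (df = 58), equal formats meet the printed rule with probability below 10⁻⁶ at every SD, against 99.9%, 97% and 86% with −20. With a one-sided 0.05 limit at 15 per group, the −20 row becomes 97%, 85% and 69%. The percentages move with the assumptions; the contradiction does not.

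**5. The sections side by side, primary outcome only.**

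| Section | Question asked |
|---|---|
| Objectives | Superiority: infographic above PLS above scientific summary |
| Sample size | Detect a 40% difference |
| Claiming of the non-inferiority | Non-inferiority; superiority assigned to secondary outcomes |
| Table 1 | Kruskal-Wallis/ANOVA |

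**The case against.** The strongest reply is that this is notation. Margins are often quoted as magnitudes, and the section's title, its use of a lower limit, its naming of the intervention first and its stated aim all point to infographic minus control with −20%. Few analysts would apply +20%. That is probably right about the cause, and it limits the practical harm. It does not repair the text. The trial also has a genuine superiority hypothesis, so a positive 20% is not absurd on its face, and no other section settles the sign.

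Several stronger readings are tempting but not supported:

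- *The rule would certify an inferior infographic.* This needs control minus infographic, a strained reading given the order in which the section names the groups. It is noted only for completeness.
- *The printed rule could never be met.* It is almost never met when formats are equal, but at the planned 40-point advantage it is met in 94%, 75% or 56% of trials under the assumptions above.
- *The plan does not allocate its tests.* It does: non-inferiority to the primary outcome, superiority to the secondary ones. The problem is that this allocation conflicts with *Objectives*.
- *Testing both claims on one outcome is itself an error.* It is not. For a single comparison, non-inferiority and then superiority can be read from the same interval without an alpha penalty.

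**Conclusion.** The point stands in two parts. First, the primary decision rule is wrong as printed: on the natural reading it requires the infographic to be better by more than 20%, contrary to the stated aim, and the reverse subtraction does not rescue it. This follows from direction alone. Its size (about 0% against 94%, 75% or 56% when formats are equal) rests on the assumed interval, SDs and percentage-point unit, and is illustrative. An omitted minus sign is the likely explanation.

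Second, the allocation of non-inferiority to the primary outcome conflicts with the superiority alternative in *Objectives*, with the 40% planning difference, and with a Table 1 entry that cannot test a margin. This is a conflict between sections, not evidence that either claim is illegitimate.

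The sign must be corrected before analysis; the conflict should be resolved at the same time.

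**What to change.** 1. In *Claiming of the non-inferiority*, state that non-inferiority is claimed if the lower limit of the confidence interval for the difference in mean score, infographic minus control, is greater than **minus** 20%, for each of PLS and scientific summary. The sponsor should confirm the unit (percentage points of the 10-point score, which would be −2 points, or relative) and the confidence level. The section states neither.
2. Reconcile that section with *Objectives*. One workable form is to test non-inferiority first and then superiority from the same interval, for each comparison.
3. Add the interval-based comparison to the Understanding row of Table 1.
4. In *Sample size*, if non-inferiority is confirmed as the primary claim, say that the stated 80% power applies to the 40% superiority difference only, because the margin was not used.

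Cost: the correction to the rule is wording only, as are the sentence on the order of claims and the table entry. Whether 15 per group is adequate for the non-inferiority claim depends on an SD the document does not give. With −20, the chance of a claim for equal formats falls below 80% at SD 20 and 25, so confirming non-inferiority as primary may prompt the sponsor to revisit the sample size.
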